2 STUDY OBJECTIVES AND DESIGN

2.1 Objectives

2.1.1 Primary Objective

To evaluate the following in HIV-negative participants who have completed at least 5 months (22 weeks) treatment for drug-susceptible pulmonary TB and who test negative for acid fast bacilli (AFB) on sputum smear microscopy prior to vaccination (participants unable to produce sputum, and considered asymptomatic by the investigator, may be considered *Mtb* negative):

- Efficacy of H56:IC31 compared to placebo in reducing the rate of recurrent TB disease (relapse or reinfection)

2.1.1.1 Primary Endpoint

- Rate of TB disease recurrence (relapse or reinfection), defined as TB diagnosed by confirmation of *Mtb* by culture of sputum, during the period starting 14 days after the 2nd vaccination (V6= Day 70) and ending 12 months after the 2nd vaccination (V8= Day 421)

2.1.2 Key Secondary Objective

To evaluate the following in HIV-negative participants who have completed at least 5 months (22 weeks) treatment for drug-susceptible pulmonary TB and who test negative for AFB on sputum smear microscopy prior to vaccination (participants unable to produce sputum, and considered asymptomatic by the investigator, may be considered *Mtb* negative):

- Safety of H56:IC31 compared to placebo

2.1.2.1 Key Secondary Endpoints

- Solicited adverse events and all adverse events occurring the first 14 days after each of the 1st and 2nd vaccinations
- Serious adverse events including medically important events occurring after the 1st vaccination through the end of the study

2.1.3 Other Secondary Objectives

To evaluate the following in HIV-negative participants who have completed at least 5 months (22 weeks) treatment for drug-susceptible pulmonary TB and who test negative for AFB on sputum smear microscopy prior to vaccination (participants unable to produce sputum, and considered asymptomatic by the investigator, may be considered *Mtb* negative):

- Trends towards efficacy of H56:IC31 compared to placebo in reducing the rate of TB disease relapse
- Trends towards efficacy of H56:IC31 compared to placebo in reducing the rate of TB disease reinfection
- Antigen-specific cell-mediated immune responses to H56:IC31
- Humoral immune responses to H56:IC31

2.1.3.1 Other Secondary Endpoints

- Rate of TB disease relapse, defined as participants meeting the primary endpoint of TB disease recurrence, AND determined by whole genome sequencing (WGS) of the *Mtb* isolate to be the same strain of *Mtb* as in the participant's original isolate from the time of diagnosis
- Rate of TB disease reinfection, defined as participants meeting the primary endpoint of TB disease recurrence, AND determined by WGS of the *Mtb* isolate to be a different strain than in the participant's original isolate from the time of diagnosis
- Antigen-specific cell-mediated immune responses by whole blood intracellular cytokine staining (WB ICS) at baseline (V3= Day 0), and 14 days after the 2nd vaccination (V6= Day 70) in the immunogenicity cohort

- Humoral immune responses by IgG ELISA of plasma samples taken from the immunogenicity cohort at baseline (V3= Day 0) and 14 days after the 2nd vaccination (V6= Day 70)

2.1.4 Exploratory Objectives

To evaluate the following in HIV-negative participants who have completed at least 5 months (22 weeks) treatment for drug-susceptible pulmonary TB and who test negative for AFB on sputum smear microscopy prior to vaccination (participants unable to produce sputum, and considered asymptomatic by the investigator, may be considered *Mtb* negative):

- Trends towards efficacy of H56:IC31 compared to placebo in reducing the rate of recurrent TB disease by exploratory efficacy endpoint definitions (Section 2.1.4.1)
- Transcriptomic signatures of inflammation or associated with TB disease recurrence
- Immunological correlates of risk and correlates of protection for TB disease recurrence
- Humoral immune responses to H56:IC31 in participants with TB recurrence diagnosis compared to the participants in the control cohort

2.1.4.1 Exploratory Endpoints

- Rate of TB disease recurrence (relapse or reinfection), defined as participants meeting the primary endpoint of TB disease recurrence AND participants who started TB treatment without confirmation of *Mtb* by culture of sputum

Rate of TB disease recurrence (relapse or reinfection), defined as participants meeting the primary endpoint of TB disease recurrence based on confirmation of *Mtb* by Xpert MTB/RIF Ultra or culture of sputum

- Rate of TB disease recurrence (relapse or reinfection), defined as participants meeting the primary endpoint of TB disease recurrence AND participants diagnosed between 30 days after the 1st vaccination and 14 days after the 2nd vaccination, based on confirmation of *Mtb* by culture of sputum
- Transcriptomic signatures (RNA analysis) and cellular composition (flow cytometry) of whole blood etc. at baseline (V3= Day 0) and at TB recurrence diagnosis
- Blood subset counts of whole blood (supports the RNA analysis) at baseline (V3= Day 0) and at TB recurrence diagnosis
- Antigen-specific cell-mediated immune responses by peripheral blood mononuclear cells (PBMC) ICS at baseline (V3= Day 0) and 14 days after the 2nd vaccination (V6= Day 70) and at TB recurrence diagnosis
- Humoral immune responses by IgG ELISA of plasma samples at baseline (V3= Day 0) and 14 days after the 2nd vaccination (V6= Day 70) and at TB recurrence diagnosis

2.2 Design

This is a phase 2, double-blind, randomized (1:1), placebo-controlled study with 2 parallel groups:

- H56:IC31 (investigational vaccine)
- Placebo

900 HIV-negative adults with a diagnosis of drug-susceptible pulmonary TB are planned to be included, recruited from TB clinics with established relationships to the study sites see Table 2-1.

5 study sites in South Africa: 2 sites from the [REDACTED] and three in Cape Town at [REDACTED] and [REDACTED].

1 study site in Tanzania (TZ): 1 site at [REDACTED].

Table 2-1 Treatment Groups and Number of Participants

Number of Doses	Treatment Assignment N (planned)		Total N (planned)
	H56:IC31 5 µg H56/ 500 nmol IC31	Placebo	
All randomized participants in study 2 x 0.5 mL (Days 0, 56) intramuscularly in deltoid	450	450	900
First 150 randomized participants across all sites Safety cohort subgroup	75	75	150
First 100 randomized participants [REDACTED] sites only Immunogenicity cohort subgroup and control cohort	50	50	100

For the summary schedule of participant evaluations, see Table 3.1. For a flowchart showing the study design, see Figure 2-1.

Screening Visits 1 and 2

The 1st screening visit (V1) must be conducted ≤ 7 days after the start date of the TB treatment. The 2nd screening visit (V2) must be conducted ≥ 5 months (22 weeks) after the start date of TB treatment. The end of TB treatment is expected to be 6 months (24 weeks) after the start of TB treatment and may not be extended beyond 28 weeks. At V1 informed consent will be obtained and inclusion and exclusion criteria (applicable for V1) will be assessed, by review of medical history. Demographics, height, weight, smoking history, Xpert MTB/RIF result or AFB smear positive result from the TB clinic (at MMRC Xpert MTB/RIF testing is performed at the site), and self-reported HIV status will be assessed. 2 separate sputum samples will be obtained and stored (frozen) for later comparison to

recurrent isolates by WGS at OSR, Italy. During the 5-month period between V1 and V2, the study staff will regularly liaise with screened participants, staff from the TB clinics and community health care workers to monitor TB treatment compliance and continued eligibility for study participation.

In- and exclusion criteria will be assessed at V2, by review of medical history, physical examination (complete), vital signs, pregnancy testing (all females) and HIV testing. For eligible participants, 2 separate sputum samples will be obtained, and safety laboratory tests (blood) and urinalysis (dipsticks) will be performed. One AFB smear for microscopy using the Auramine technique will be created from each of the sputum samples.

Upon written approval from the sponsors and relevant approvals for protocol amendment v5.0, the activities scheduled for the 1st screening visit (V1) will be performed on the same day as (or together with) the 2nd screening visit (V2). At a combined screening visit (V1 and V2) the participant must have completed at least 5 months (22 weeks) of TB treatment and while TB treatment must be ongoing.

Randomisation and follow-up

The TB treatment must still be ongoing at V3= Day 0, and it must be verified that the participant is tested *Mtb* negative, i.e. both sputum samples from V2 must be negative by smear AFB microscopy. Participants unable to produce sputum, but considered asymptomatic by the investigator, may be considered *Mtb* negative and eligible for inclusion. All inclusion and exclusion criteria will be assessed or re-assessed, by review of medical history, physical examination (symptom directed), weight, vital signs, pregnancy testing (all females) and confirmation of negative HIV status from V2.

Eligible participants, after verification of vaccination eligibility criteria, see Section 3.5, will be randomized (1:1) to receive either H56:IC31 or placebo, and the 1st vaccination will be administered.

Before administering the 2nd vaccination on V5= Day 56, physical examination (symptom directed), weight, vital signs, pregnancy testing (all females), TB symptoms screen, and vaccination eligibility criteria will be assessed, see Section 3.5 and 6.1.

After each vaccination, it will be assessed if immediate AEs occurred within 60 minutes (for details see Section 3.6.3.1), TB signs and symptoms training will be performed, and diary cards will be handed out to the participants.

There will be short-term follow-up visits after each vaccination on V4= Day 14 and V6= Day 70, with weight, vital signs, TB symptoms screen and review of diary cards. Solicited AEs including injection site reactions and concomitant medications (CM), and spontaneously reported AEs, including serious AEs and AEs of special interest, will be assessed and recorded. If there is suspicion of TB disease, 2 separate sputum samples will be obtained, and the case verification procedure (see details below) for recurrent TB disease will be initiated.

For the safety cohort (= the first 150 randomized participants across all sites), see Table 2-1, there will also be safety laboratory testing on V4= Day 14 and V6= Day 70. For the remaining participants, there will only be laboratory safety testing at screening (V2), or at the ET Visit, if within 14 days after the investigational medicinal product (IMP) administration.

At the long-term follow-up visit on V7= Day 238, there will be a TB symptoms screen including weight and recording of serious adverse events (SAEs) and AEs of special interest. If there is suspicion of TB disease, 2 separate sputum samples will be obtained, and the case verification procedure (see details below) for recurrent TB disease will be initiated.

At the last study visit, V8= Day 421, whether or not there is suspicion of TB disease, 2 separate sputum samples will be obtained from all participants to identify missed cases, see Section 3.6.1. At this visit a negative Xpert MTB/RIF Ultra does not need to be verified by culture for participants with no clinical TB symptoms. Furthermore, SAEs and AEs of special interest will be assessed and recorded, if any.

Immunogenicity / immunology laboratory samples: PBMCs and plasma for ICS and IgG ELISA will be collected from all participants on V3= Day 0, V6= Day 70 and at suspicion of TB recurrence, as defined for the STB Visit, ET Visit or V8. Whole blood for RNA analysis and blood subset counts (to support the RNA analysis) will be collected from all participants at V3= Day 0 and at suspicion of TB recurrence, as defined for the STB Visit, ET Visit or V8, see Table 3-2.

For the immunogenicity cohort at the [REDACTED] TZ sites only (= first 50 randomized participants at [REDACTED] and first 50 randomized participants at [REDACTED] = in total 100 participants), see Table 2-1, whole blood will be collected and stimulated for WB ICS on V3= Day 0 and V6= Day 70, see Table 3-2. For the remaining participants and sites, there will be no collection of whole blood for WB ICS.

The immunogenicity cohort at the [REDACTED], TZ sites also serves as control cohort, see Section 7.4.5 and Table 2-1. Therefore there will be collection on V8= Day 421, of PBMCs and plasma for ICS and IgG ELISA and whole blood for RNA analysis and blood subset counts. These samples will be control samples for the corresponding immunology samples taken from participants under diagnosis of recurrent TB during the study, see Table 3-2.

TB signs and symptoms training will take place at all visits and telephone calls (TCs) from V3= Day 0 and onwards, and TB symptom screening at all visits and TCs from V4= Day 14 and onwards. The TC1 to TC5 will take place on the following days: Day 154, 196, 280, 322 and 364. If there is suspicion of TB at any of these occasions, based on the TB symptoms screening, 2 separate sputum samples will be obtained, and the case verification procedure (see details below) for recurrent TB disease will be initiated at a Suspected TB (STB) visit.

[figure not shown]
Participants who are withdrawn from the study within 6 months after the last product administration, will be contacted at least 6 months after the last product administration for recording of SAEs and AEs of special interest.

Referral for diagnosis and management of recurrent TB is triggered by the investigator based on clinical suspicion of recurrent TB. Participants will not be withdrawn from the study based on this referral but will be withdrawn if *Mtb* positive by culture in the study or if the referral clinic diagnoses recurrent TB and starts TB treatment. The case verification procedure is initiated at a STB Visit.

Case verification procedure for recurrent TB disease:

- 2 separate sputum samples are obtained:
 - 1 sputum sample is tested by Xpert MTB/RIF Ultra
 - The same sputum sample and the second sputum sample are both sent for culture
 - The remainder of the 2 separate sputum samples is stored (frozen) as 2 separate samples for later analysis by WGS if recurrent TB is confirmed
- The participant is HIV tested (including CD4 count for participants who test HIV positive) and immunology samples are taken, see Table 3-2.
- If *Mtb* positive by culture in the study, the participant is informed of TB test results, referred to TB treatment management as per national programme guidelines (if not previously done), and is withdrawn (at the ET Visit) due to verified recurrent TB.
- If *Mtb* negative by culture in the study the participant is informed of TB test results, continues in the study and no ET Visit is completed.
- If *Mtb* negative by culture or the study culture result is pending, but the referral clinic diagnosed recurrent TB and started TB treatment, 2 additional sputum samples must be collected as soon as possible for repeat *Mtb* testing by culture, and the participant is withdrawn from the study.

Figure 2-1 Study Flow Diagram

Upon written approval of the Sponsors and relevant approvals for the Protocol Amendment v5.0, participants may be screened at a combined V1 and V2. This visit will be scheduled when the participant has completed at least 5 months (22 weeks) of TB treatment and TB treatment must be ongoing.

An internal data review committee, consisting of the coordinating principal investigator (PI), the site PIs and the medically responsible person from each of the co-sponsors, will convene during the study to review the blinded reported SAEs, AEs including AEs of special interest, injection site reactions and laboratory safety test results to identify any possible safety issues when:

- The first 150 participants across all sites have received their 1st vaccination and the 14 days safety follow-up data is available
- The first 150 participants across all sites have received their 2nd vaccination and the 14 days safety follow-up data is available

An independent data safety monitoring board (DSMB) will be established, consisting of a panel of independent experts, who will operate according to a DSMB charter. The DSMB will be convened if:

- A stopping rule is triggered
- The internal data review committee requests a DSMB meeting based on their review of the safety data

For more details on the internal data review committee review of safety data and the DSMB procedures, please see sections 5.1.4 and 6.2.

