3 STUDY PROCEDURES

3.1 Schedule of Participant Evaluations

Written informed consent must be obtained before any screening procedures are performed.

A Summary Schedule of Evaluations depicting all visit-specific procedures is provided in Table 3-1.

Upon written approval from the sponsors and relevant approvals for protocol amendment v5.0, the activities scheduled for the 1st screening visit (V1) will be performed on the same day as (or together with) the 2nd screening visit (V2). At this combined screening visit (V1 and V2) the participant must have completed at least 5 months (22 weeks) of TB treatment and TB treatment must be ongoing. Activities scheduled for both V1 and V2 do not need to be repeated.

Table 3-1 Summary Schedule of Participant Evaluations

	Study Day / Suspected TB (STB Visit) / Early Termination (ET Visit) / Telephone Call (TC) / Visit Window \pm days															
	Visit 1 ¹ Screening ≤ 7 days after Start of TB treatment	Visit 2 ¹ Screening ≥ 5 months (22 weeks) after start of TB treatment	Visit 3 ¹ Day 0 Before end of TB treatment	Visit 4 Day 14	Visit 5 Day 56	Visit 6 Day 70	TC 1 Day 154	TC 2 Day 196	Visit 7 Day 238	TC 3 Day 280	TC 4 Day 322	TC 5 Day 364	Visit 8 Day 421	STB ¹⁵ Visit NA	ET ¹⁶ Visit NA	
Informed consent	X															
Demographics	X															
Medical history, medication & smoking history	X	X	X ⁵													
In- / exclusion criteria	X	X	X ⁵													
Weight	X (incl. height)	X	X	X	X	X		X				X	X ⁹		X	
Complete physical examination	X															
Symptom directed physical examination - and if needed extra safety tests			X ⁵		X ⁵											
Vital signs (Pre- and post-vaccination on vaccination days) - and if needed extra safety tests	X	X	X	X	X	X									X ⁸	
Urine pregnancy test (β HCG) - all females	X	X	X ⁵		X ⁵											
HIV testing	X (self-reported)	X											X ¹⁰	X	X ¹⁰	
Urine analysis ¹¹		X ³		X ⁶		X ⁶									X ^{6,8}	
Serum chemistry ¹²		X ³		X ⁶		X ⁶									X ^{6,8}	
Hematology ¹³		X ³		X ⁶		X ⁶									X ^{6,8}	
WB ICS – only immunogenicity cohort (whole blood)			X ^{5,7}			X ⁷										
ICS & IgG ELISA (PBMCs and plasma)			X ⁵			X							X ^{7,10}	X	X ¹⁰	
RNA analysis (whole blood)			X ⁵										X ^{7,10}	X	X ¹⁰	
Blood subset count supporting RNA analysis (whole blood)			X ⁵										X ^{7,10}	X	X ¹⁰	
Vaccination eligibility criteria verification			X ⁵		X ⁵											
Randomization			X ⁵													
Vaccination		X			X											

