- 10) At a participant's last study visit (V8 or ET Visit), 2 separate sputum samples are collected, and 1 sputum sample is tested with Xpert MTB/RIF Ultra. If *Mtb* positive by Xpert MTB/RIF Ultra, the same sputum sample is sent for culture together with the 2nd sputum sample, and the participant returns to the site for HIV testing and immunology sample collection. The remainder of the 2 sputum samples is frozen for later analysis by WGS. The participant is referred to TB treatment management as per national programme guidelines and HIV management if HIV positive. If *Mtb* negative by Xpert MTB/RIF Ultra and no TB signs or symptoms are observed, the sputum samples are not culture confirmed and no HIV testing and no immunology sample collection will be performed. Note: If there is clinical suspicion of TB at V8, all V8 activities will be conducted and not a STB visit since at V8 two separate sputum samples for *Mtb* testing will be obtained from all participants even if there is no clinical suspicion of TB. This is to ensure that no cases of recurrent TB disease are missed during the trial. One sputum sample will be tested by Xpert MTB/RIF ultra. If *Mtb* negative by Xpert MTB/RIF ultra but there are clinical TB signs or symptoms, verification by culture testing will be requested from the laboratory and both of the sputum samples will then be processed for culture. In this instance HIV testing and immunology sample collection should also be performed at V8.
- 11) Urine analysis: *urine protein (dipstick)*, *glucose (dipstick)*, *leukocytes (dipstick)*, and *blood (microscopy if positive by dipstick)*
- 12) Serum chemistry: *AST, ALT, ALP, GGT, total bilirubin, creatinine*
- 13) Hematology: *hemoglobin, hematocrit, white cell count with differential, and platelet count*
- 14) Participants who are withdrawn from the study within 6 months after the last product administration, are contacted at least 6 months after the last product administration for recording of SAEs and AEs of special interest
- 15) A STB Visit is conducted if the investigator based on the TB symptom screen, decides to proceed with verification of recurrent TB. If recurrent TB is not verified, the participant stays in the study. In this case, if triggered by a TB symptom screen later in the study, another STB Visit would be conducted.
- 16) If withdrawal is due to verified recurrent TB, the only study events at the ET Visit are SAEs and AEs of special interest and date of withdrawal

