3.6.2 Immunogenicity and Immunology Laboratory Evaluations

A summary of immunogenicity and immunology assays to be performed on blood specimens is shown in Table 3-2.

For the immunogenicity cohort at the [REDACTED] sites only (= first 50 randomized participants at [REDACTED] and first 50 randomized participants at [REDACTED] = in total

100 participants), see Table 2-1, whole blood will be collected for WB ICS. For the remaining participants and sites, there will be no collection of whole blood for WB ICS.

For all participants in the study, the immunogenicity / immunology samples, assays, endpoints, blood volumes, study days of collecting samples and names of laboratories analyzing the samples are shown below in Table 3-2.

Staff at the clinical study site will refer to the most current version of the Laboratory Manual (provided under separate cover) for further instructions and additional information on specimen including sputum collection and processing.

Table 3-2 Summary of Immunogenicity and Immunology Laboratory Evaluations

Sample Type	Assay	Immunogenicity/ Immunology Endpoint	Approximate Blood Volume (per Visit)	Study Days	Name and Location of Analysis Laboratory
Whole blood	WB ICS	Secondary endpoint ¹ (Primary immunogenicity endpoint)	6 mL	0 ¹ , 70 ¹	██████████
Plasma (obtained from PBMC)	IgG ELISA	Secondary endpoint ¹	Plasma (3 mL) obtained from PBMC	0 ¹ , 70 ¹	██████████
Plasma (obtained from PBMC)	IgG ELISA	Exploratory endpoint ²	Plasma (3 mL) obtained from PBMC	0 ² , 70 ² , 421 ⁵ , STB ³ , ET ⁴	██████████
Whole blood	RNA analysis	Exploratory endpoint ²	2.5 mL	0 ² , 421 ^{1,5} , STB ³ , ET ⁴	██████████
Whole blood (DLC iCE)	Blood subset count (support of RNA analysis)	Exploratory endpoint ²	At least 0.5 mL collected in a 2.0 mL tube	0 ² , 421 ^{1,5} , STB ³ , ET ⁴	██████████
PBMC	ICS	Exploratory endpoint ²	50 mL	0 ² , 70 ² , 421 ^{1,5} , STB ³ , ET ⁴	██████████

- 1) Participants in immunogenicity cohort (1st 50 randomized at ██████████ and 1st 50 randomized at ██████████)
- 2) All participants in study
- 3) Participants if STB Visit is conducted
- 4) Participants who have not already had this at a STB Visit which resulted in verification of recurrent TB and who are Xpert Ultra MTB/RIF positive at the ET Visit
- 5) Participants who are Xpert Ultra MTB/RIF positive at Visit 8 (Day 421)

For further details on the purpose of the assays and the immunogenicity/immunology endpoints, see Section 7.4.

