7.4.5 Exploratory Immunology at TB Recurrence - Control Samples

The exploratory immunology samples to be taken at the time of evaluation of TB recurrence, from participants with a suspected diagnosis of recurrent TB disease will be: PBMC and plasma for ICS and IgG ELISA and whole blood for RNA analysis and Blood subset counts (that support the RNA analysis), see Table 3-2.

For the analysis of these samples, “control samples” from a “control cohort” are needed.

The immunology samples taken at V8= Day 421 from the participants in the immunogenicity cohort (excluding participants with recurrent TB, if any), see Table 2-1, will be these “control samples”. See Table 3.1.

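### Tables 3-1 and 3-2 do not match the Day 421 control sampling required by Sections 2.2 and 7.4.5: no control IgG ELISA is listed, and footnote 10 makes no exception for the control cohort

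*Protocol*

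**What the plan says.** **The requirement.** Protocol Section 2.2 gives the immunogenicity cohort (50 participants at each of two sites) a second role as control cohort. At V8, "Therefore there will be collection on V8= Day 421, of PBMCs and plasma for ICS and IgG ELISA and whole blood for RNA analysis", together with blood subset counts. Their purpose is explicit: "These samples will be control samples for the corresponding immunology samples taken from participants under diagnosis of recurrent TB during the study". Section 7.4.5 repeats this, naming "The immunology samples taken at V8= Day 421 from the participants in the immunogenicity cohort" as the control samples and leaving out anyone with recurrent TB. Section 2.1.4 sets an objective that depends on them: "Humoral immune responses to H56:IC31 in participants with TB recurrence diagnosis compared to the participants in the control cohort".

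**Table 3-1.** The V8 cells for PBMC and plasma, RNA and subset count each carry footnotes 7 and 10. Footnote 7 means membership of the immunogenicity cohort. Footnote 10 covers the last study visit of any participant. If Xpert is negative and there are no TB signs or symptoms, "no HIV testing and no immunology sample collection will be performed". It mentions no exception for the cohort. Its closing note says that symptomatic Xpert-negative participants at V8 should have immunology samples taken, as does Section 3.6.1.

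**Table 3-2.** Day 421 carries footnotes 1 and 5 for RNA, subset count and PBMC ICS. It carries footnote 5 alone in the exploratory IgG ELISA row. The secondary IgG row lists Days 0 and 70 only. Footnote 1 is the immunogenicity cohort; footnote 5 is "Participants who are Xpert Ultra MTB/RIF positive at Visit 8 (Day 421").

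**SAP.** Section 1 places the V8 exploratory immunology samples outside its scope, as described elsewhere, and points to Appendix A. Appendix A covers only whole-blood ICS at Days 0 and 70.

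**The concern.** The intended control is a cohort member who reaches V8 without recurrence, so typically Xpert-negative and without symptoms. That is the person footnote 10 says is not sampled, and the person the Table 3-2 IgG row leaves out.

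Two things are at stake. The humoral comparison of cases with the control cohort has no Day 421 control assay listed. And if a site acts on the footnote 10 sentence, the control draw is missed. For RNA and subset counts a missed draw cannot be made good, because no other sample is scheduled from these participants after TB treatment ends.

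**Working it through.** The plan states no control count, so the main check is a comparison of texts, followed by a short calculation of scale.

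**1. The four assays side by side**

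| Assay | Control at Day 421 under 2.2 and 7.4.5 | Table 3-1 V8 footnotes | Table 3-2 Day 421 footnotes | Cohort listed at Day 421 in Table 3-2 | Other scheduled post-treatment sample from the cohort |
|---|---|---|---|---|---|
| IgG ELISA (exploratory) | required | 7, 10 | 5 | no | Day 70 |
| PBMC ICS | required | 7, 10 | 1, 5 | yes | Day 70 |
| RNA | required | 7, 10 | 1, 5 | yes | none |
| Subset count | required | 7, 10 | 1, 5 | yes | none |

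The IgG row is the only one in which Table 3-2 contradicts Sections 2.2 and 7.4.5 outright. Table 3-2 says the ELISA plasma is obtained from the PBMC draw, and that draw is listed for the cohort at Day 421. The gap is therefore in the assay listing, not necessarily in the specimens.

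**2. Which draws fall after TB treatment.** Inclusion criterion 7 requires at least 22 weeks of treatment, still ongoing, at Day 0, and at most 28 weeks in total. Treatment therefore ends by (28 − 22) × 7 = Day 42 at the latest. Day 0 samples are on treatment and Day 70 samples are after it. PBMC and plasma are drawn at Day 70; RNA and subset counts are not.

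**3. How to read footnotes 7 and 10 together.**
- If both had to hold, suspected cases outside the cohort would not be sampled at V8, although Section 2.2 says they are.
- If footnote 10 prevailed, footnote 7 would have no effect, since sampling triggered at V8 already covers everyone.
- The coherent reading is cohort member, or triggered under footnote 10.

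The table does not state this, and its paired footnotes work both ways. In the whole-blood ICS row, footnotes 5 and 7 at V3 must both apply. In the ET laboratory cells, SAP Section 7.2.3 treats footnotes 6 and 8 as alternatives.

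**4. Footnote 5 against footnote 10.** Footnote 10 and Section 3.6.1 call for immunology samples at V8 from symptomatic Xpert-negative participants. Table 3-2 footnote 5 covers Xpert-positives only.

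**5. Endpoint wording.** None of the exploratory immunology endpoints in 2.1.4.1 (RNA, subset count, PBMC ICS, IgG) names a Day 421 control time point.

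**6. Scale.** Inputs from Protocol Section 7.5: 10% drop-out, 4% per year placebo recurrence, VE 60%, hence 1.6% on vaccine.
- Cohort at V8: 100 × 0.90 = 90.
- Pooled recurrence: (4% + 1.6%)/2 = 2.8%.
- Controls: 90 × (1 − 0.028) = 87.5, about 87.
- Placebo rate 2% or 8% (the range in Section 1.1): pooled 1.4% or 5.6%, giving 88.7 or 85.0.
- Drop-out 0% or 20% (assumed range): 97.2 or 77.8.
- Expected recurrences in the trial: 450 × 0.9 × (0.04 + 0.016) = 22.7, agreeing with the stated 23.

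**The case against.** The best defence is that the plan does schedule these controls. Footnote 7 appears on the V8 immunology cells but not on the V8 HIV-testing cell or the ET immunology cells, so it was evidently put there to bring in the control cohort. Table 3-2 keeps the cohort for three of the four assays. SAP Section 1 lists the V8 exploratory samples, IgG ELISA included, separately from those taken on suspicion of recurrence. The Laboratory Manual and the separate analysis description may settle the matter, and neither is available here. The IgG gap rests on one superscript in a table read by a program, and the humoral objective names no Day 421 time point.

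Most of this stands. A reader might infer that the protocol forbids the control draw and leaves all four assays with almost no comparator. The documents do not support that: it requires following one sentence of footnote 10 while ignoring footnote 7, Table 3-2 and Sections 2.2 and 7.4.5. Nor is Day 421 the only post-treatment control sample for every assay, since PBMC and plasma are also taken at Day 70.

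The defence does not remove the mismatch. The IgG row still omits the controls that Section 7.4.5 places at V8, and the no-sampling sentence still has no exception.

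**Conclusion.** The protocol is inconsistent as written, within limits.

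- **Definite:** Table 3-2 lists no Day 421 IgG ELISA for the control cohort, contrary to Sections 2.2 and 7.4.5. The plasma should exist if the PBMC draw is made.
- **Ambiguous:** footnote 10 could lead a site to skip the V8 control draw. The loss would be irrecoverable only for RNA and subset counts.
- **Definite, smaller:** Table 3-2 footnote 5 omits symptomatic Xpert-negative participants at V8.

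About 87 controls are involved (85 to 89 across placebo rates of 8% to 2%). That figure assumes the cohort has the trial-wide drop-out and recurrence rates, and is for scale only. The conclusion also assumes the superscripts are as printed and that paired footnotes are read as alternatives. Only exploratory endpoints are touched; the primary, secondary and safety analyses are not.

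**What to change.** 1. Table 3-2, exploratory IgG ELISA row: change the Day 421 footnote from 5 to 1,5.
2. Table 3-1 footnote 10: add that the no-sampling sentence does not apply to the immunogenicity (control) cohort, whose V8 PBMC, plasma, RNA and subset-count samples are taken whatever the Xpert result or symptoms.
3. Table 3-2 footnote 5: extend it to participants with TB signs or symptoms at V8, in line with footnote 10 and Section 3.6.1.
4. Section 2.1.4.1: add the Day 421 control time point to all the exploratory immunology endpoints (RNA, subset count, PBMC ICS and IgG).

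If V8 visits are already complete, the sponsor should confirm which reading each of the two sites followed and whether control plasma was stored, and specify the IgG comparison before analysis.

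The cost is the text edits and up to about 90 ELISA runs (100 × 0.90) on plasma that Section 2.2 already plans to collect. No visit is added.
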